Project Title:

Children's Automated Respiration Monitor (ChARM) for child pneumonia diagnosis by Community Health Workers in Mali: Innovating ChARM's role in supervision, training and diagnosis, a cluster randomized control trial

Principal Investigators:

[name]

Health Advisor, Global Health Unit, International Operations, Canadian Red Cross

[name]

Director, International Program Evaluation Unit (IPE), Center for Global Child Health Epidemiologist, Pediatric Medicine Division, Hospital for Sick Children Assistant Professor of Pediatrics, Faculty of Medicine, University of Toronto

Emails: [contact] & [contact]

Addresses and Telephones:

[name] Global Health Unit, International Operations, Canadian Red Cross [name] [contact] (cell)

[name] Center for Global Child Health, Peter Gilgan Centre for Research and Learning [name] [contact] [name]

Study Location: Koulikoro and Banamba districts, Koulikoro region, Mali

Proposed project dates: December 2017 – December 2018

Project Summary

roject Summary	
Title	Children's Automated Respiration Monitor (ChARM) for child pneumonia diagnosis by Community Health Workers in Mali: Innovating ChARM's role in supervision, training and diagnosis, a cluster randomized control trial
Short Title	Children's Automated Respiration Monitor (ChARM) for child pneumonia diagnosis by Community Health Workers in Mali
Clinicaltrials.gov	NCT03457519
Design	Cluster Randomized Pragmatic Parallel Trial
	Intervention Group A - Community Health Workers (CHWs) (Basic training in CHW curriculum, ChARM training and 8-month application of the ChARM device, self-monitoring, direct observation and review of CHW routine monthly reports and drug supply sheets): 8 months, March-December 2018.
Study Duration	Intervention Group B - Community Health Workers (Basic training in CHW curriculum, ChARM training and 4-month application of the ChARM device, self-monitoring, direct observation and review of CHW routine monthly reports and drug supply sheets): 8 months,— March- December 2018.
	Control Group C - Community Health Workers (Basic training in CHW curriculum, direct observation and CHW routine monthly reports and drug supply sheets): 8 months, – March- December 2018.
	CHW and Field Monitor In-depth interviews – December 2018
	Data analysis and report writing December -January 2018

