- Intervention Group A: CHWs trained in ChARM and using ChARM as a self-monitoring tool for 8 months while counting respiratory rate of children under 5 visually using a timer.
- Intervention Group B: CHWs trained in ChARM and using ChARM as a self-monitoring tool for 4 months while counting respiratory rate of children under 5 visually using a time; then discontinue using ChARM and continue to monitor the respiratory rate visually using a timer only for the remaining 4 months.
- Control Group C: CHWs who did not receive the ChARM training and will be monitoring the respiratory rate of children under 5 visually using a timer only, as per the MoH traditional training.

Throughout the study 3 independent Field Monitors will follow each group's participants in both Banamba and Koulikoro (i.e. one Field Monitor will follow 1/2 CHWs in Group A in Banamba and 1/2 CHWs in Group A Koulikoro; the Field Monitors responsible for Groups B and C will also follow one study group each, in both areas). The Field Monitors will be responsible for both testing the accuracy of the CHWs' ability to count respiratory rate and for collecting data during the study from the CHW reports and drug records. The Field Monitors will receive the same training as the CHWs in the Intervention Groups A and B, and additional training on data collection and observation protocol. The Field Monitor will test the CHWs' capacity to count respiratory rate during three intervals:

[figure not shown]
- Before the ChARM training
- 4 months after initiating the use of the ChARM device
- 8 months after initiating the use of the ChARM device (which corresponds to 4 months after the ChARM device will be discontinued for group B).

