At each of the three measures, the Field Monitor will test CHWs on their visual respiratory rate counting capacity using a timer against the ChARM automated readings and review supporting data sources. To maintain the study observation periods comparable, and save on the additional logistics costs, the intervention will be rolled out in Koulikoro 1 month after it has been rolled out in Banamba. Therefore, for the 2nd and 3rd direct observation the Field Monitors will begin first in Banamba and then one month later in Koulikoro. This will allow time for the Field Monitors to carry out the site visits required for each district for each of the measurements (approximately 24 visits per Field Monitor per district). As a result, the 2nd and 3rd measure for Groups A and B and C in Banamba will be at 4 months and 8 months, and the same groups in Koulikoro will be measured one month later, but still at 4 and 8 months.

The qualitative evaluation will be undertaken only in the Intervention Groups A and B using In-depth Interviews (IDIs) with CHWs, Field Monitors and the Technical Director of the Health centre responsible for the CHWs. In total 25 IDIs will be carried out. The Study Coordinator will be responsible for supporting the research and qualitative researcher who will be carrying out the IDIs. In total, anticipated number of IDIs are:

- Field Monitors 3 IDIs, one interview with each one
- Technical Director of Health Centre (Directeur Technique du Centre/CSCom) (DTCs) 10 IDIs (5 in Banamba and 5 in Koulikoro)
- Community Health Workers 12 IDIs

Figure I: RCT Flow Chart

4. Randomization

An epidemiologist not directly involved in the research project will perform randomization of clusters. Due to the nature of the intervention, blinding is not possible, however to ensure reduced measurement bias, data on the effect of the intervention will be collected by independent data collectors; not involved in the intervention delivery. The unit of randomization will be the community health worker.

5. Study Setting

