Acute Respiratory Illness (ARI) Case fatality rate

Secondary outcomes:

Respiratory rate assessment accuracy

Proportion of pneumonia cases detected and treated by CHWs

Proportion of suspected severe pneumonia cases referred by CHWs to the CSCom

Proportion of suspected cases of pneumonia in the community who sought care from a CHW

Accuracy in drug management and procurement requests

Sample size:

48 clusters with average size of 50 suspected ARI cases per cluster per arm (over 8 months) are sufficient to detect a 30% reduction in the ARI case-fatality rate (from 20% at baseline), with 80% power and 5% significance. Differences in all secondary outcomes are powered above 80% within this sample size.

iCCM Curriculum Training: Intervention & Control sites

Participants: CHWs in Koulikoro and Banamba districts (n=148)

Time frame: Completed as part of CRC program implementation in Mali (December 2016 – August 2017)

Responsibility: CRC/MoH Mali Trainers

Training Material: Ministry of Health iCCM curriculum for CHWs -18-day curriculum including classroom instruction and hands on training.

Intervention Training: Intervention sites

Participants: CHWs in Koulikoro (n≅49) and Banamba (n≅49) districts.

Time Frame: After iCCM curriculum training; 9 months-1month for training CHWs in ChARM and 8 months for monitoring.

Responsibility: External Trainers and Study coordinator

- A. CHWs trained in ChARM and the self-monitoring data collection format.
- B. Submission of regular MoH monthly reports, consultation referral forms, drug supply forms.
- C. In-depth interviews for CHWs, Field Monitor and the Technical Director of Health Centres (Directeur Technique du Centre/CSCom) on their perception of ChARM tool and recommendations for future use as a teaching tool and/or scale up by the MoH.

Control Sites

CHWs in Koulikoro and Banamba districts (n=49)

Time frame: 8 months-including initial measurement of respiratory rate counts using a timer against ChARM's automated reading and subsequently repeating the measurement twice during the study.

- A. Pneumonia diagnosis as per usual practice of visually counting respiratory rate using a respiratory timer.
- B. Submission of regular monthly reports, consultation/referral reports and drug supply reports for review by Field Monitors.

12. Data Processing and analysis

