Data (described in section 16) will be collected on paper by the Field Monitors. Data will be entered in the ChARM database by the field monitors and study coordinator, after the data is entered it will be checked for consistency and/or missing responses. Inconsistencies and/or omissions will be flagged and communicated to interviewers for clarification.

The data entry forms, databases and interface will be developed using ODK. The data entry forms will employ range and consistency checks and logical skips to improve interview efficiency and minimize data entry errors. Special arrangements will be made to enforce referential integrity of the database so that all data tables are related to each other.

The trial data will be analyzed as "Intention to treat" (ITT).

After successful completion of data transfer agreements between the Academic Partner in Mali and SickKids, deidentified data will be transferred to SickKids using the SickKids-based secure online file transfer protocol managed by the Research Information Technology team at SickKids. Once the data have arrived at SickKids, it will be secured behind the SickKids firewall, which is backed up by the hospital system (SickKids server/cloud). Data will be encrypted and will only be made available to [name] and his SickKids' research personnel who have successfully completed the TCPSII Course on Research Ethics training and have been added to the REB application for this study. For quantitative data analysis STATA version 13 and for qualitative data analysis Nvivo will be used.

13. Field Supervision and Quality Control

An in-country project team composed of a part-time Study coordinator and three Field Monitor, with support from the project team, will coordinate project activities. The Study coordinator will assist with the training of Community Health Workers in the intervention and control clusters along with three Field Monitors and the CRC/MRC program staff. The project team will also be responsible for all the logistics and monitoring support of project activities and the Study coordinator will be responsible for the overall oversight.

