Information obtained during this study will only be transferred in an anonymized form. The national and international regulatory agencies and sponsoring agencies may request access to the medical or other confidential records of participating subjects, but the identity of subjects will remain confidential. The final study report with aggregate anonymized data will be shared with the Minister of Health-Mali, without identifying the individual CHWs. All study records will be kept confidential in keeping with the stipulated requirements by the ethics boards of the Hospital for Sick Children and Ethics Committee of the Faculty of Medicine, Pharmacy, Odontology and Somatology of Mali (FMPOS).

Figure III: Timeline of the Trial

Month of Study - Number	0	1	2	3	4	5	6	7	8	9	10	11	12
Month of Study - Name	 	J	F	M	A	M	J	J	A	S	0	N	D
Cluster Randomization	X	-	1	171	7.1	171	-	-	7.1			11	
MOU – Koulikoro Regional Health	X												
Directorate	21												
Orientation of CSCom District	X												
Technical Coordinator													
In-Country Study Team	X												
identification													
Training of Study Team		X											
1 ST data collection of all CHWs			X										
Training of CHWs in Intervention			X										
Groups A and B in ChARM													
Groups A and B initiate use of			X										
ChARM													
2 nd data collection of all CHWs in							X						
Banamba													
2 nd data collection of all CHWs in								X					
Koulikoro													
Interim data analysis								X					
3 rd data collection of all CHWs in											X		
Banamba													
3rd data collection of all CHWs in												X	
Koulikoro													
Individual in-depth interviews in												X	
Banamba													
Individual in – depth interviews in													X
Koulikoro													
In-depth interviews with Field										X			
Monitors and MoH DTCs													
Quarterly reporting			X			X			X			X	
Final data analysis												X	X
Preparation of Final report												X	X

Annexes: (Attached)

Annex #	Document Name	Document
Annex 1: CHWs Tools	Outil de projet:	W
	Fiche d'auto surveillance pour les Agents de Santé Communautaire du protocole ChARM	Fiche de Auto Surveillance_ASC_29
	Ministère de Santé: Rapport Mensuel d'Activités du Site ASC	RMA ASC_25- 06- 2016_amenage.pdf
	Fiche Individuelle de Prise en Charge de L'Enfant Malade	Version w ord fiche PEC 25 juin 2016 (Enr
	Fiche de Reference et Contre-Reference	Fiche de reference et contre reference A

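### Section 13 can be read as giving the outcome assessors a part in training the CHWs, which Section 4 rules out, and Figure III schedules the assessors' interviews on ChARM's effectiveness before the third test, against the text

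*Protocol*

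**What the plan says.** Section numbers are those printed in the body of the protocol, which differ from its table of contents.

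- **Safeguard.** Section 4 (Randomization) says blinding is not possible and that, to reduce measurement bias, "data on the effect of the intervention will be collected by independent data collectors; not involved in the intervention delivery".
- **Who collects.** Section 3 (Trial Methodology and Sample Size) gives the monitors both tasks: "The Field Monitors will be responsible for both testing the accuracy of the CHWs' ability to count respiratory rate and for collecting data during the" (the sentence goes on to name the sources, CHW reports and drug records). Section 11 (Data Collection) confirms this and assigns one monitor to each group.
- **Who trains.** Section 13 (Field Supervision and Quality Control): "The Study coordinator will assist with the training of Community Health Workers in the intervention and control clusters along with three Field Monitors". Red Cross programme staff are named in the same sentence. In Section 11, the block on intervention training reads "Responsibility: External Trainers and Study coordinator", with no mention of the monitors. Section 3 says "The Field Monitors will receive the same training as the CHWs in the Intervention Groups A and B", and Sections 10 and 11 also describe them as attending the training.
- **When the monitors are interviewed.** Figure III has a row beginning "In-depth interviews with Field" (Field Monitors and DTCs) marked in month 9. The Project Summary dates "CHW and Field Monitor In-depth interviews" December 2018. Section 6 (Study Duration) names the third test as the first activity of Phase III and the interviews as the second. It says the interviews with monitors and DTCs concern how effective they perceive ChARM to be in improving CHW accuracy.

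**The concern.** The counting test addresses the stated primary objective, although counting accuracy is listed among the secondary outcomes. The monitors administer it and record both readings on site, and each knows the arm because each follows one group. What Section 4 offers in place of blinding is that the assessors have no hand in delivering the intervention. If they help to train Groups A and B, they have a stake in how those CHWs perform and the safeguard fails.

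The interview date raises a related issue. Asking unblinded assessors whether ChARM works, and then sending them to take the final measurement, invites them to commit to a view beforehand. It also costs information: an interview held before the 8-month round cannot draw on that round, nor on how Group B performs at the end of its months without the device.

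**Working it through.** No power or alpha figure bears on this point. The check compares the text and reads Figure III by column.

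**1. Do the monitors train CHWs?**

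For a trainer role:
- Section 13 sets out the duties of the project team, not who is to be trained.
- Its sentence groups the monitors with Red Cross programme staff, whom the protocol nowhere describes as ChARM trainees.
- Figure III puts training of the study team in month 1 and ChARM training of CHWs in month 2, so the monitors would already be trained by then.
- Section 11 says the basic iCCM training ended in August 2017, before the study team was identified (month 0). ChARM training is the only CHW training that Figure III schedules.

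For a trainee role only:
- Section 11 gives the intervention training to external trainers and the coordinator.
- Section 10 defines the counting trainer, the ChARM trainer and the Field Monitors as separate roles, with the monitors attending training given by the other two.
- Section 3 calls the monitors independent and says they receive the training.
- Section 13 refers to training in control clusters as well, yet Group C gets no ChARM training, so the sentence is loosely worded.

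The trainer reading is the more natural one for the Section 13 sentence taken in its place. The other sections point the other way. The result is a conflict, not an established trainer role.

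**2. When are the monitors interviewed relative to the tests?**

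The header of Figure III and the eight rows checked each have 14 columns (a label and months 0 to 12), so the marks can be placed by position:

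| Row | Month |
|---|---|
| First data collection | 2 |
| Second, Banamba / Koulikoro | 6 / 7 |
| Field Monitor and DTC interviews | 9 |
| Third, Banamba / Koulikoro | 10 / 11 |
| CHW interviews, Banamba / Koulikoro | 11 / 12 |

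- By Figure III, the interviews precede the third test by 10 − 9 = 1 month in Banamba and 11 − 9 = 2 months in Koulikoro.
- By the Project Summary, December 2018 is month 12 of Figure III, so they follow it by 12 − 10 = 2 months in Banamba and 12 − 11 = 1 month in Koulikoro.
- Group B stops using ChARM once tested in month 6 or 7. At month 9 it has gone 9 − 6 = 3 months (Banamba) or 9 − 7 = 2 months (Koulikoro) without the device, against the planned 4.

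The order within Figure III does not depend on how its months map to the calendar.

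**3. Reach.** The third round covers about 148 CHWs and all three monitors. The documents give nothing from which to compute a bias.

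**The case against.** The strongest reply is that the trainer role rests on one loosely worded sentence. Every section that defines the monitors' job makes them independent assessors who receive training, and the block that assigns the intervention training leaves them out. A reader might infer from Section 13 that the monitors do train Groups A and B. The documents do not establish that. They leave it open, in a sentence that touches the stated safeguard.

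A reader might also infer from Figure III that the design is to interview assessors before the last test. That is true of the figure only; the Project Summary and the order of activities in Section 6 say otherwise. What stands is a contradiction in timing.

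A third tempting reading is that the Study coordinator breaches the safeguard, because that person shares responsibility for the intervention training and "Data will be entered in the ChARM database by the field monitors and study coordinator". The double role is explicit, but Section 4 speaks of who collects the data. The coordinator receives paper forms and enters them, and is not named as a field collector, so nothing is contradicted. Taking the coordinator off data entry would leave the unblinded monitors alone entering their own results, and masking by arm would be difficult with one monitor per group.

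Finally, the monitors already know the arm, and the reference is ChARM's automated reading, recorded beside the CHW's count. This limits the room for assessor influence without removing it. That an interview a month or two earlier adds bias is plausible but not demonstrable from the documents.

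**Conclusion.** The point holds in a limited form and is minor. Section 13, on its more natural reading, conflicts with the independence that Section 4 promises, while Sections 3, 10 and 11 support that independence. Figure III conflicts with the Project Summary and Section 6 on when the monitors are interviewed. If Figure III is followed, all three unblinded assessors give an opinion on the effect one to two months before the last measurement, and the interviews miss the 8-month round.

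The conclusion assumes that the Section 13 sentence refers to training still to come, and that the Figure III marks sit in their printed columns, which the column count supports. No magnitude of bias is claimed.

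**What to change.** 1. In Section 13, state that Field Monitors take no part in training CHWs and attend only as trainees. Section 11 already gives the intervention training to external trainers and the coordinator, so no new staff are needed.
2. In Figure III, move the Field Monitor and DTC interviews to after the last Koulikoro test (late month 11 or month 12), in line with the Project Summary and Section 6.

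The cost is one sentence, one timeline entry and slightly less help on training days. The move also brings 3 + 10 = 13 of the 25 planned interviews into the closing weeks, alongside the CHW interviews and the final analysis, so the qualitative researcher's time should be checked.

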16.1. Field Monitors

The Field Monitors (described above) will be responsible to collect data at three different time periods, before the intervention, 4 months after the intervention begins and 8 months after the intervention begins. There will be one Field Monitor each for Groups A, B and C who will cover those groups in both districts. They will be practicing health

professionals and have participated in the 1-day ChARM training in which they will receive in-depth understanding of the required data collection forms and the ChARM device. Field Monitors will conduct 3 site visits to test the CHWs respiratory rate counting ability using a timer against the ChARM automated reading and record both readings. They will review and document the number of cases assessed for pneumonia, treated and/or referred by CHWs during the three testing periods.

Data Collection

i) Quantitative Data Collection:

Written informed consent will be taken from participating Community Health Workers in the Intervention and Control Groups, and from parents and caregivers of all children under five who will have their respiratory rates counted using the ChARM device. It will be made clear that eligible participants are under no obligation to participate in this study. In addition, the time burden associated with being involved in this study will be clearly outlined during the consent process.

Data from the CHW self-monitoring sheets filled out by Intervention Groups A and B will be reviewed and documented by the Field Monitor. The Field Monitor will also measure all CHWs respiratory rate counting capacity using ChARM as a global standard and collect routine CHW data three times during the study. This routine data is found in both the CHW monthly reports and the consultation/referral forms. Data from drug supply forms filled out by CHWs will also be collected to identify any variations that may occur due to more accurate pneumonia diagnosis by CHWs as a result of using ChARM and to triangulate this data with the consultation forms and other sections of the monthly report.

ii) Oualitative Data Collection:

Qualitative data collection will only take place in the intervention Groups A and B. Written, informed consent will be taken from CHWs, Field Monitors and MoH Technical Director of Health Centre (Directeur Technique du Centre/CSCom) participating in in-depth interviews. (Consent Forms - Annex 3, Questions for In-depth interviews - Annex 4).

Outcomes:

Primary outcome:

Acute Respiratory Illness (ARI) Case fatality rate

Secondary outcomes:

Respiratory rate assessment accuracy

Proportion of pneumonia cases detected and treated by CHWs

Proportion of suspected severe pneumonia cases referred by CHWs to the CSCom

Proportion of suspected cases of pneumonia in the community who sought care from a CHW

Accuracy in drug management and procurement requests

Sample size:

48 clusters with average size of 50 suspected ARI cases per cluster per arm (over 8 months) are sufficient to detect a 30% reduction in the ARI case-fatality rate (from 20% at baseline), with 80% power and 5% significance. Differences in all secondary outcomes are powered above 80% within this sample size.

iCCM Curriculum Training: Intervention & Control sites

Participants: CHWs in Koulikoro and Banamba districts (n=148)

Time frame: Completed as part of CRC program implementation in Mali (December 2016 – August 2017)

Responsibility: CRC/MoH Mali Trainers

Training Material: Ministry of Health iCCM curriculum for CHWs -18-day curriculum including classroom instruction and hands on training.

Intervention Training: Intervention sites

Participants: CHWs in Koulikoro (n≅49) and Banamba (n≅49) districts.

Time Frame: After iCCM curriculum training; 9 months-1month for training CHWs in ChARM and 8 months for monitoring.

Responsibility: External Trainers and Study coordinator

- A. CHWs trained in ChARM and the self-monitoring data collection format.
- B. Submission of regular MoH monthly reports, consultation referral forms, drug supply forms.
- C. In-depth interviews for CHWs, Field Monitor and the Technical Director of Health Centres (Directeur Technique du Centre/CSCom) on their perception of ChARM tool and recommendations for future use as a teaching tool and/or scale up by the MoH.

Control Sites

CHWs in Koulikoro and Banamba districts (n=49)

Time frame: 8 months-including initial measurement of respiratory rate counts using a timer against ChARM's automated reading and subsequently repeating the measurement twice during the study.

- A. Pneumonia diagnosis as per usual practice of visually counting respiratory rate using a respiratory timer.
- B. Submission of regular monthly reports, consultation/referral reports and drug supply reports for review by Field Monitors.

12. Data Processing and analysis

Data (described in section 16) will be collected on paper by the Field Monitors. Data will be entered in the ChARM database by the field monitors and study coordinator, after the data is entered it will be checked for consistency and/or missing responses. Inconsistencies and/or omissions will be flagged and communicated to interviewers for clarification.

The data entry forms, databases and interface will be developed using ODK. The data entry forms will employ range and consistency checks and logical skips to improve interview efficiency and minimize data entry errors. Special arrangements will be made to enforce referential integrity of the database so that all data tables are related to each other.

The trial data will be analyzed as "Intention to treat" (ITT).

After successful completion of data transfer agreements between the Academic Partner in Mali and SickKids, deidentified data will be transferred to SickKids using the SickKids-based secure online file transfer protocol managed by the Research Information Technology team at SickKids. Once the data have arrived at SickKids, it will be secured behind the SickKids firewall, which is backed up by the hospital system (SickKids server/cloud). Data will be encrypted and will only be made available to [name] and his SickKids' research personnel who have successfully completed the TCPSII Course on Research Ethics training and have been added to the REB application for this study. For quantitative data analysis STATA version 13 and for qualitative data analysis Nvivo will be used.

13. Field Supervision and Quality Control

An in-country project team composed of a part-time Study coordinator and three Field Monitor, with support from the project team, will coordinate project activities. The Study coordinator will assist with the training of Community Health Workers in the intervention and control clusters along with three Field Monitors and the CRC/MRC program staff. The project team will also be responsible for all the logistics and monitoring support of project activities and the Study coordinator will be responsible for the overall oversight.

The Field Monitors will be responsible for ensuring quality control in data collection as well as maintain close liaison with the Community Health Workers and the field project staff to have access to project data if necessary. They will also ensure timely and accurate paper data transfer from field to the Study coordinator who will also have overall responsibility for the on-ground management and supervision of the trial.

14. Data Safety Monitoring

A data and safety monitoring board (DSMB) will be convened with three individuals, [name], at the Hospital for Sick Children, [name], Mali, [name] [name], Mali, with expertise in the clinical area of the trial and [name], a Biostatistician at the Hospital for Sick Children. The DSMB will have the mandate of making an independent, fully informed assessment of the progress of the trial. It will make recommendations to the trial PI as to whether to continue, amend or terminate the trial. The DSMB will be provided de-identified data at 2nd and 6th month of data collection. The identity of study groups will be masked unless the DSMB determines that the identities of the groups are necessary for their decision making. The DSMB may also make recommendations / escalate issues to the REB at SickKids (primary organization) and Comité d'éthique de la Faculté de Médecine, de Pharmacie et d'Odonto-Stomatologie de Mali (FMPOS).

Function / Responsibilities of the DSMB:

- Assess and monitor the trial from an ethical perspective
- Assess the quality and completeness of interim data
- Review recruitment and participant retention data
- Review protocol and deviations from the Standard Operating Procedures
- Review any individual events considered significant
- Make recommendations regarding trial continuation, amendments or termination
- Assess the need for stopping the trial prematurely based on strong evidence of unintended harm or external evidence for all or any of the following.
- a) Failure to adhere to the research protocol and non-compliance with goals for recruitment and retention.
- b) Any factors that might affect the study outcome or compromise the confidentiality of the trial data (such as protocol violations, unmasking, etc.); and,
- c) Factors external to the study such as scientific or therapeutic developments that may impact participant safety or the ethics of the study.

15. Ethical Approval, Consent Process, Confidentiality, and Safety

Ethical Approval

The study proposal will be submitted for ethical approval to Comité d'éthique de la Faculté de Médecine, de Pharmacie et d'Odonto-Stomatologie de Mali (FMPOS), and the Research Ethics Board at The Hospital for Sick Children, Toronto, Canada. Subsequent to this approval, consent and agreement to participate will be obtained from the regional and district health departments of Koulikoro and Banamba in Koulikoro, Mali.

Participant Consent

Written informed consent will be obtained from mothers and/or fathers of children under five at the time of their consultation with the CHW. If the mother is not able to give consent, her husband or other adult family member present will be invited to give consent to participate in the study. The CHW will explain risks and benefits to potential enrollees and participants will be informed that they have the right to withdraw from the study at any time and that there are no penalties from doing this and this will not in any way affect their ability to receive any health care services.

Ethical issues, Benefits and Safety

Caregivers of children will be free to consent to participate or not in the study. Community Health Workers will explain that children with rapid respiratory rates will be treated on site if no complicating factors are observed, but that if there are complicating factors, children will be referred and/or treated at the next level of care. Anonymity of caregivers, their children and the community health workers and data will be ensured.

The ChARM training will be conducted in such a way that the community health workers do not feel vulnerable or persecuted in any way.

Overall, improved quality of neonatal and child care in diagnosing and treating Pneumonia are the anticipated benefits of this study which outweigh the risks in this study. Health care providers and families can refuse or are free to withdraw at any time from participating in the study and no penalties will arise from this refusal.

Confidentiality

Information obtained during this study will only be transferred in an anonymized form. The national and international regulatory agencies and sponsoring agencies may request access to the medical or other confidential records of participating subjects, but the identity of subjects will remain confidential. The final study report with aggregate anonymized data will be shared with the Minister of Health-Mali, without identifying the individual CHWs. All study records will be kept confidential in keeping with the stipulated requirements by the ethics boards of the Hospital for Sick Children and Ethics Committee of the Faculty of Medicine, Pharmacy, Odontology and Somatology of Mali (FMPOS).

Figure III: Timeline of the Trial

Month of Study - Number	0	1	2	3	4	5	6	7	8	9	10	11	12
Month of Study - Name	 	J	F	M	A	M	J	J	A	S	0	N	D
Cluster Randomization	X	-	1	171	7.1	171	-	-	7.1			11	
MOU – Koulikoro Regional Health	X												
Directorate	21												
Orientation of CSCom District	X												
Technical Coordinator													
In-Country Study Team	X												
identification													
Training of Study Team		X											
1 ST data collection of all CHWs			X										
Training of CHWs in Intervention			X										
Groups A and B in ChARM													
Groups A and B initiate use of			X										
ChARM													
2 nd data collection of all CHWs in							X						
Banamba													
2 nd data collection of all CHWs in								X					
Koulikoro													
Interim data analysis								X					
3 rd data collection of all CHWs in											X		
Banamba													
3rd data collection of all CHWs in												X	
Koulikoro													
Individual in-depth interviews in												X	
Banamba													
Individual in – depth interviews in													X
Koulikoro													
In-depth interviews with Field										X			
Monitors and MoH DTCs													
Quarterly reporting			X			X			X			X	
Final data analysis												X	X
Preparation of Final report												X	X

Annexes: (Attached)

Annex #	Document Name	Document
Annex 1: CHWs Tools	Outil de projet:	W
	Fiche d'auto surveillance pour les Agents de Santé Communautaire du protocole ChARM	Fiche de Auto Surveillance_ASC_29
	Ministère de Santé: Rapport Mensuel d'Activités du Site ASC	RMA ASC_25- 06- 2016_amenage.pdf
	Fiche Individuelle de Prise en Charge de L'Enfant Malade	Version w ord fiche PEC 25 juin 2016 (Enr
	Fiche de Reference et Contre-Reference	Fiche de reference et contre reference A
